9.2. Sample Size and Power

For this prospective analysis we will have an estimated sample size of 3,010 patients. The sample size is computed for the population with minimum representation in the total sample. 2019 rates of PRRT were 15% in this population. Using a conservative estimation of 10% PRRT administration, and erring on the side of caution, our sample size and power justification is based on approximately 300 subjects (excluding HRQoL questionnaire completion rates). By the law of the minimum, all other treatment subgroups with representation above 10% will yield greater sample size and consequently higher powers for the below-stated differences

9.2.1. Aim 1

The primary objective of Aim 1 is to evaluate changes in HRQoL over time for each treatment. Calculations are based on using the EORTC QLQ-C30 as the primary HRQoL measure. Conservatively

estimating PRRT to be administered in 10% of patients and further expecting a response rate of 60% in the study, we would expect the PRRT group may have approximately 180 patients with complete HRQoL data. Using a repeated measures design with 1 within-subject factor (time: baseline, 6 months, 12 months, and 18 months), the design achieves the following power (Table 5) to detect a time effect for the corresponding mean change. Calculations are based on assuming an autocorrelation of 0.5 between measurements, a standard deviation of 18, and using a Wilks' Lambda Approximate F Test with a 5% significance level. The power will be higher if PRRT administration amounts to more than 10% of the prospective population.

Table 5: Alternative power for changes in EORTC QLQ-C30 within PRRT treated subgroup

MEAN CHANGE IN HRQOL OUTCOMES AT BASELINE, 6, 12 AND 18 MONTHS (RANGE 0-100)*	DIFFERENCE IN MEAN HRQOL SCORE (OVER EACH TIME POINT)	POWER*
65, 62, 59, 56	3-3-3	100%
65, 63, 61, 59	2-2-2	98.3%
65, 63.5, 62, 60.5	1.5-1.5-1.5	84.3%

* THE POWER APPLIES EQUALLY TO POSITIVE OR NEGATIVE SCORING SCALES.

9.2.2. Aim 2

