The primary objective of Aim 2 is to evaluate the effect of common treatment sequences on progression-free survival. A lack of historical data on the frequency and number of different variations of treatment sequences, and progression-free survival (PFS) differences by treatment and line of treatment coupled with the likelihood treatment sequences will further differ between the 14 sites taking part in this study make *any realistic and meaningful* sample size and power calculations impossible. Analyses for this aim will be exploratory, and will leverage the use of time-varying covariates in combination with the conditional Cox regression model proposed by Prentice, Williams, and Peterson (PWP) as a means of addressing the heterogeneity evidenced in the data. However, to put into perspective potential PFS differences that may be detected between two treatments using purely hypothetical situations, the below table summarizes power achieved for varying combinations of median PFS differences and number of patients per treatment arm. Calculations are based on the following assumptions: 1:1 treatment allocation, 48 months of uniform accrual and 12 months of follow-up, no loss to follow-up or switching treatments, unadjusted for confounders, and using the Lakatos approximation for a two-sided log-rank test with a 5% significance level.

Table 6: Power determination for changes in median PFS

Median PFS		N Per Treatment Arm	Power
Treatment 1	Treatment 2		
12 months	24 months	45	0.79
		50	0.83
24 months	36 months	175	0.80
		190	0.83

9.2.3. Aim 3

The primary objective of Aim 3 is to evaluate renal toxicity associated with the administration of PRRT as measured by creatinine clearance loss over time. We are expecting 2 mL/min/1.73m² annual decline in creatinine clearance based on averaged long-term follow-up with the most common PRRT isotope 177-Lu [34]. The repeated measures design with 180 subjects and 1 within-subject factor (time: baseline, 6 months, 12 months, and 18 months) achieves 100% power to detect creatinine clearance loss of 2 mL/min/1.73m² by 6 months, 4 mL/min/1.73m² by 12 months and 6 mL/min/1.73m² by 18 months, when the Wilks' Lambda approximate F test is used with a significance level of 0.05, and assuming an

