autocorrelation of 0.5 from one time point to the next and a standard deviation of 5 mL/min/1.73m². Should the standard deviation become unreasonably high in the order of 15 mL/min/1.73m², our sample size is large enough to achieve 99% power under the same parameter settings. In order to test Bonferroni-corrected pairwise differences, the individual tests will achieve 99.6% power to detect a clearance loss of 2 mL/min/1.73m² between two time points. The Bonferroni-corrected tests will be set at a significance level of 0.05/6.

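### Aim 3 is powered for a creatinine clearance loss twice as fast as the annual decline the protocol expects, using a sample size taken from questionnaire completion

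*Protocol*

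**What the plan says.** The primary objective of Aim 3 (Protocol 9.2.3) is to "evaluate renal toxicity associated with the administration of PRRT as measured by creatinine clearance loss over time". Table 4 lists renal function as the Aim 3 primary outcome and marks it as powered.

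Section 9.2.3 first states an expected decline of 2 mL/min/1.73m² per year, based on long-term follow-up with the most common isotope. It then gives these power statements:

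- "The repeated measures design with 180 subjects and 1 within-subject factor" (baseline, 6, 12 and 18 months) has 100% power for losses of 2, 4 and 6 by 6, 12 and 18 months. The test is the Wilks' Lambda approximate F at 0.05, with SD 5 and an "autocorrelation of 0.5 from one time point to the next".
- If the SD rose to about 15, "our sample size is large enough to achieve 99% power under the same parameter settings".
- Each Bonferroni-corrected pairwise test (0.05/6) has 99.6% power for a loss of 2 between two time points. No SD is attached to this figure, and it follows directly after the SD 15 sentence.

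The 180 is derived in 9.2.1 for the questionnaire outcome: 10% receive PRRT, and "further expecting a response rate of 60% in the study" the authors conclude that "the PRRT group may have approximately 180 patients with complete HRQoL data". The opening of 9.2 gives the number before that reduction: "our sample size and power justification is based on approximately 300 subjects (excluding HRQoL questionnaire completion rates").

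**The concern.** A decline of 2 per year is 1 by 6 months, 2 by 12 and 3 by 18. The profile used for power is twice that at every visit, so the power figures answer a question about a decline of 4 per year. The noncentrality parameter grows with the square of the effect, so halving the loss cuts it to a quarter.

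Three further features make the paragraph hard to use. The n belongs to a different outcome. The correlation wording fits more than one structure. The pairwise figure can be read as applying at SD 15, where it does not hold. This paragraph is the only power justification for the Aim 3 primary outcome, so a reader relying on it would misjudge what the study can detect at its own expected effect.

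**Working it through.** **Inputs (Protocol 9.2 to 9.2.3).** Four visits; n = 180, or about 300 before questionnaire response (10% of 3,010; 300 × 0.60 = 180); SD 5 or 15; correlation 0.5; overall α = 0.05; pairwise α = 0.05/6.

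**Overall test.** With one group and four visits, Wilks' Lambda is equivalent to Hotelling's T² on three contrasts. Power comes from the noncentral F with 3 and n − 3 degrees of freedom and noncentrality λ = n·d′(CΣC′)⁻¹d, where d holds the changes between successive visits, C is the contrast matrix and Σ the covariance matrix. For a steady loss of δ per visit this reduces to:

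- equal correlation of 0.5 for all pairs: λ = 10·n·δ²/SD²
- lag-1 decay (0.5, 0.25, 0.125): λ = (31/6)·n·δ²/SD² ≈ 5.17·n·δ²/SD²

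The critical F is 2.656 for n = 180 and 2.635 for n = 300.

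**Step 1: which structure did the protocol use?** Table 5 uses the same test with n = 180, correlation 0.5 and SD 18.

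| Change per visit | Stated | Equal correlation | Lag-1 |
|---|---|---|---|
| 3 | 100% | 100% | 99.4% |
| 2 | 98.3% | 98.4% | 81.3% |
| 1.5 | 84.3% | 84.8% | 54.2% |

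Equal correlation reproduces Table 5 closely; lag-1 does not.

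**Step 2: the Aim 3 figures as stated (δ = 2, n = 180).** At SD 5, power is 100% under either structure. At SD 15 with equal correlation, λ = 10 × 180 × 4/225 = 32.0 and power is 99.9%, so the stated 99% is met. Under lag-1, λ = 16.5 and power is 93.7%.

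**Step 3: the expected rate (2 per year, δ = 1).**

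| SD | n | Equal: λ | Equal: power | Lag-1: λ | Lag-1: power |
|---|---|---|---|---|---|
| 5 | 180 | 72.0 | about 100% | 37.2 | about 100% |
| 15 | 180 | 8.0 | 64% | 4.1 | 36% |
| 15 | 300 | 13.3 | 88% | 6.9 | 58% |

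**Step 4: pairwise tests.** This is a paired t test with SD of the difference = SD·√(2(1 − 0.5)) = SD, and noncentrality = loss·√n/SD. At n = 180 the two-sided critical t at 0.05/6 is 2.668.

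- Loss 2, SD 5: 2 × 13.416/5 = 5.37, power 99.6%, as stated.
- Loss 2, SD 15: 1.79, power 19%.
- Loss 1, SD 5: 2.68, power 51%.

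At the expected annual rate, a loss of 1 is the six-month difference, which applies to the three adjacent pairs of visits. A loss of 2 is the twelve-month difference. Under lag-1, power for a 2-unit loss at SD 5 is 95.6% for visits 12 months apart and 91.6% for visits 18 months apart.

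**The case against.** **A reader might infer that the 99% is an arithmetic error.** The Aim 3 phrase about correlation from one time point to the next reads naturally as lag-1, which gives 93.7%. The document does not support calling the 99% wrong. No structure is named. Equal correlation reproduces Table 5, is consistent with a single 99.6% for all the pairwise tests, and gives 99.9% at SD 15. For the stated 2/4/6 losses, n = 300 also gives at least 99.6% under either structure. What stands is that the wording is ambiguous.

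**A reader might infer that Aim 3 is underpowered.** This does not follow either. At the base-case SD of 5, overall power at the expected rate is still about 100%, and the protocol itself calls SD 15 unreasonably high. The low overall figures arise only in that stress case. It is nevertheless a case for which the protocol makes an explicit claim, and the 51% pairwise figure arises at SD 5.

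**The n of 180 is conservative.** This is right: a smaller n can only lower the computed power. Section 7.1 also draws on the enrollment questionnaire for this outcome, and section 6.2 anticipates that creatinine may be poorly populated in the common data model, so some reduction from 300 is reasonable. But the outcome does not need four completed surveys. A 60% questionnaire response is not an estimate of how many patients will have serial creatinine, and the protocol gives no reason for carrying it over.

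**The missing SD is editorial.** Largely so, since 99.6% reproduces exactly at the base-case SD of 5. Its position after the SD 15 sentence still invites a misreading, and the true figure there is 19%.

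**Conclusion.** The point holds as an inconsistency between the expected effect and the powered effect: 2 per year against 4 per year. At the protocol's own expected rate with n = 180 and equal correlation, power at SD 15 is 64%, not 99%, and pairwise power for the six-month loss at SD 5 is 51%, not 99.6%. Overall power at SD 5 is essentially unaffected. The n of 180 is a mismatch in the opposite direction. With about 300 patients, power at SD 15 is 88%, before any loss for missing laboratory values.

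These results assume a linear decline, the stated test and levels, and complete data at all four visits. Equal correlation is inferred from its fit to Table 5; under lag-1 decay, the SD 15 figures are 36% (n = 180) and 58% (n = 300). The issue should be corrected because the outcome is primary and marked as powered, but it does not show that the design fails.

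**What to change.** In Protocol 9.2.3:

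1. Recompute power with losses consistent with 2 mL/min/1.73m² per year (1, 2 and 3 by 6, 12 and 18 months). If 2/4/6 is really intended, restate the expected annual decline and its basis so that the two agree.
2. Replace 180 with the expected number of PRRT patients with serial creatinine: about 300 before laboratory missingness, less a stated allowance.
3. Name the correlation structure, and use the same description in 9.2.1 and 9.2.3.
4. Report overall power at both SD 5 and SD 15.
5. Attach an SD and an interval between visits to the pairwise figure.

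The cost is a recalculation and a rewritten paragraph. Recruitment, data collection and the planned analysis do not change.

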9.3. Addressing confounding

With a large, proposed sample size of approximately 3,000 patients, we will minimize the effects of confounding on treatment effect estimates by adjusting for factors associated with treatment selection within the context of multivariable models. Known and hypothesized factors associated with treatment selection include but are not limited to the following: sociodemographic (age, sex, race, ethnicity, marital status, income), health status (BMI, smoking history, comorbidities), disease (site, stage, grade, nodal status), prior therapy use (PRRT, everolimus, sunitinib, liver-directed therapies, chemotherapy, surgery), and patient-reported preferences, attitudes, beliefs and experience of care. Determination of confounding factors that may warrant adjustment will be guided by the results from the multinomial logistic regression models evaluating factors associated with selection of treatment regimens (Aim 2). Furthermore, the use of time-dependent variables for treatment and potential confounders (where appropriate) will minimize the effects of survivor treatment selection bias.

As a novel project aimed to evaluate the complex interplay between patient, disease, and treatment factors on toxicity, HRQoL, and survival outcomes, the statistical analysis plan will be refined once descriptive information from Aims 1 and 2 is available for consented patients. For example in Aim 3, PRRT sits amongst a growing number of therapeutic options in metastatic well-differentiated NETs, including pharmacological (i.e.: mTOR inhibitor everolimus and the tyrosine kinase inhibitor sunitinib), hormonal and liver-directed therapies (i.e.: embolization (bland, chemo, radio)), and surgical approaches. Therefore, we need to be mindful of this multimodal treatment algorithm wherein patients may undergo a variety of treatment options at tumor progression(s).

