2.1. Purpose

The purpose of this project is to partner with patients on CER to achieve the goal of mitigating toxicity and optimizing effectiveness and sequencing of therapy for patients with NETs.

In order to achieve this overall goal, we have four specific aims. Aim 1 addresses the patient question of ‘what therapy would be best to try next?’ in the context of symptom burden and quality of life. Aim 2 addresses patient concerns surrounding the question of ‘If I were to take this option now, what treatment options will be closed off to me in the future’, by examining patient and tumor factors associated with overall survival and disease progression. Aim 3 leverages the data obtained in aims 1 and 2 to inform a comparative effectiveness study of contemporary concern, with a focus on patient-centered quality of life and toxicity outcomes. Aim 4 will aid dissemination of our study results and contribute to PCORnet rare disease infrastructure.

AIM1: To describe the frequency of treatment regimens received by line of therapy, and examine their association with symptom burden and changes in 6, 12 and 18 month HRQoL outcomes. The influence of patient preferences, beliefs, attitudes, and experience of care on choice of these treatment regimens will also be examined.

Expected outcomes of aim 1: This aim will enable the ascertainment of patient-reported outcomes (PROs) related to the experience of symptom burden and toxicities for various therapies (and combination treatments) and explore the patient’s attitudes and beliefs that impact the choice of treatment sequencing beyond the basis of clinical and tumor characteristics. Descriptive analyses of these important PROs (that do not exist in the patient’s EMR will determine what combinations of therapy are being used, and the changes in symptoms and HRQoL associated with these therapeutic choices.

AIM 2: To examine the association of patient, clinical, and tumor characteristics on the selection of first-line and beyond treatment regimens and compare the effects of common treatment sequences on frequency of subsequent treatments received and outcomes of overall survival and disease progression.

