9. STATISTICAL ANALYSIS PLAN

9.1. General Statistical Approach

Continuous variables will be summarized using descriptive statistics such as mean, standard deviation, median, minimum and maximum. Categorical variables will be summarized by count and percentage. Group comparisons will be assessed using chi-squared or Fisher's exact tests for categorical variables, and an analysis of variance or Kruskal-Wallis tests for continuous variables where appropriate. Adjustment for covariates listed in Tables 2 and 3 will be explored for each analysis as needed to account for potential confounding effects. Time-dependent covariates will be incorporated to capture changes in covariates across time, as necessary. Inclusion of random effects to account for potential clustering of patients treated at the same study site will be explored. Depending on the rate and pattern of missing data, multiple imputation methods may be considered to account for data missing at random or attributable to non-ignorable drop-out [56]. Planned study outcomes are summarized in Table 4.

9.1.1. Aim 1

Mixed effects regression models will be utilized to assess changes in HRQoL and symptoms within and between groups (i.e.: different treatment regimens) over time. Random effects will be employed to account for the longitudinally correlated nature of repeated questionnaire measurements. Should completion of questionnaires deviate from the planned assessment time points, a spatial power covariance structure will be included to account for the unequal time spacing between assessments within a patient.

9.1.2. Aim 2

Multinomial logistic regression models will be used to identify which patient, clinical, and tumor characteristics (Table 2), and patient attitudes and beliefs (Table 3) influence selection of treatment regimens for each line of treatment. The conditional Cox regression model proposed by Prentice, Williams, and Peterson (PWP) will be used to simultaneously model the gap times between initial diagnosis and first progression and between subsequent progressions as a function of the prognostic factors of interest for progression-free survival. The baseline hazard is expected to differ for first-line therapy and for subsequent lines of therapy, thus event-specific estimates will be obtained. A robust sandwich estimator will be used to account for potential dependencies within patients. Overall survival will be evaluated using a Cox regression model.

9.1.3. Aim 3

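### Section 9.3's time-dependent regression cannot estimate whole-sequence or earlier-line effects when progression is both a result of one treatment line and the trigger for the next

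*Protocol*

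**What the plan says.** Aim 2 (Protocol 2.1) is to "compare the effects of common treatment sequences on frequency of subsequent treatments received and outcomes of overall survival and disease progression". Section 8 extends the ordering question to all three aims. Section 8.3 compares PRRT before versus after embolization and chemotherapy on renal toxicity, progression, symptoms and HRQoL.

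The models are fixed in 9.1: mixed effects regression for HRQoL, a Prentice-Williams-Peterson (PWP) gap-time model for progression, Cox regression for overall survival, and the same approach for Aim 3. On covariates that change, 9.1 says: "Time-dependent covariates will be incorporated to capture changes in covariates across time, as necessary".

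Section 9.3 controls confounding by "adjusting for factors associated with treatment selection within the context of multivariable models" and adds that "the use of time-dependent variables for treatment and potential confounders (where appropriate) will minimize the effects of survivor treatment selection bias". Its named factors include "disease (site, stage, grade, nodal status), prior therapy use (PRRT, everolimus, sunitinib, liver-directed therapies, chemotherapy, surgery". The list is open-ended, but progression or current disease status is not named in it. The section closes by noting that "patients may undergo a variety of treatment options at tumor progression(s".

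No weighting method or g-method appears in the text. A time-dependent propensity score stands in the abbreviation list but is not used in the sections shown.

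**The concern.** A variable that earlier treatment changes, and that then decides the next treatment, has two roles. As a confounder of the next line it must be controlled. As a consequence of the earlier line it must not be conditioned on if that line's full effect is wanted. One outcome regression cannot do both, whether or not its covariates are time-dependent.

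Progression is the obvious case here for survival and HRQoL. Symptom score can play the same part, as can renal function for creatinine clearance if it drives the choice of the next line. Treatment order is the study's central question. A first line that works by delaying progression could appear to do little, or a useful later line could look harmful because it is given to patients who have progressed.

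**Working it through.** **1. The plan's own figures.** The only sequence-related numbers are in Table 6 (9.2.2), which assumes no switching and no confounding. With λ = ln 2 / median, the event probability under 48 months' accrual plus 12 months' follow-up is p = 1 − (e^(−12λ) − e^(−60λ))/(48λ). For 12 versus 24 months, p = 0.831 and 0.617, so 45 per arm gives 45 × 1.448 = 65.2 events. Lakatos-type integration gives power 0.795, 0.835, 0.801 and 0.832 against the stated 0.79, 0.83, 0.80 and 0.83. The table reproduces, and the point is not about its arithmetic.

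**2. Are both links in the protocol?**
- Progression leads to the next line: the closing statement of 9.3 quoted above. Section 6.2 also codes progression by whether treatment changed.
- Earlier line affects progression: 1.1.3 describes therapy as given to suppress tumor growth, with a new modality tried when benefit fades.

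Both are present.

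**3. Illustration on a 0–100 outcome.** All effect sizes are assumed, because the protocol gives none. First line A0 has probability 0.5 and latent prognosis U is N(0,1). Progression: logit P(L) = −A0 + U. Next line: logit P(A1) = −1 + 2L. Outcome: Y = 65 + 2·A0 + 4·A1 − 8·L − 6·U + N(0, 15²). N = 2,000,000. The weak setting halves the A0→L, U→L, L→A1, L→Y and U→Y coefficients. The target is both lines given versus neither.

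| Setting | Truth | L omitted | L adjusted | Weighted |
|---|---|---|---|---|
| Moderate | 7.60 | 1.40 | 5.01 | 7.56 |
| Weak | 6.47 | 5.11 | 5.80 | 6.44 |
| Moderate, no U | 7.86 | 4.05 | 5.94 | 7.79 |
| A0 does not affect L | 6.01 | 0.00 | 5.99 | 6.00 |
| L does not drive A1 | 7.62 | 7.53 | 4.99 | 7.53 |

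In the moderate setting the true separate effects are 3.59 (A0) and 4.01 (A1).
- Omitting L gives 3.04 and −1.64, so the sign of A1 is reversed.
- Adjusting for L gives 1.00 and 4.01. The later line is right. A0 loses 3.59 − 2.00 = 1.59 that works through progression and a further 2.00 − 1.00 = 1.00 from the collider path through U. The sum, 2.59, equals 7.60 − 5.01.

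The last two rows show that both links are needed. Without the first, adjustment is correct. Without the second, omission is correct up to simulation error.

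**4. Survival version (also assumed).** First line cuts the progression hazard by 40%, the death hazard rises fourfold after progression, the second-line HR for death is 0.70, and latent prognosis SD runs from 0 to 1. First line's total HR is 0.85–0.92. Adjusted for progression and second line it becomes 0.98–1.13. Second line's HR is 1.43–3.70 with progression omitted and 0.66–0.74 with it adjusted.

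**5. Which remedy works.** In step 3 some non-progressors receive A1, so weights for a fixed A0/A1 pair exist. If second line is given only at progression they do not: such weighting returned a second-line HR of 1.06–1.38 against 0.70. Weighting for adherence to a strategy (A, then B at progression) recovered the first-line contrast: 0.86–0.90 against 0.87–0.89.

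**The case against.** **Survivor bias.** A reader might infer that the quoted sentence is false. It is not. It promises control of survivor treatment selection bias, and time-dependent treatment does address that. The gap is that nothing else in 9.3 covers feedback between treatment and confounder, although the section opens by claiming that confounding will be minimized.

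**Biased either way.** It is tempting to say that every treatment effect is biased whether or not progression is adjusted for, and that the plan makes both lines look bad. The documents do not support this. The latest line, adjusted for progression at its start, comes out close to the truth. The harmful-looking second line and the erased first line come from two mutually exclusive models, and the protocol commits to neither.

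**Different estimands.** In the survival version, first line acts on death only through progression, so its direct effect is truly 1.0. A value near 1 after adjustment is mostly a different estimand. A Cox model with first line alone recovers the total effect, and 9.1 brings in time-dependent covariates only where needed. This stands for first line considered alone. It does not rescue a comparison of sequences, which needs both lines.

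**Reach.** Power in 9.2.1 and 9.2.3 is for change within the PRRT group, not for sequence contrasts. Aim 2's primary progression analysis is exploratory, and for time to first progression, progression is the outcome. The protocol does not say that progression affects renal function. All this stands and limits the point.

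**Deferral.** 9.3 says the plan will be refined, comparators are not final (8.1), and a revised analytic plan is pending (Table 8, B7). However, 9.3 already names its method and claims what it will achieve, and the promised refinement names no method for this problem.

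**Conclusion.** The point holds in a limited form. For whole-sequence or earlier-line effects on overall survival and HRQoL, the regression described in 9.3 is biased under the links the protocol itself describes. Creatinine clearance is included only where renal function drives the next line.

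Under the assumed values the joint effect fell short by 2.59 of 7.60 points with progression adjusted and by 6.20 with it omitted. In the weak setting the shortfalls were 0.67 and 1.36 of 6.47. These show mechanism and direction under those assumptions. Neither size nor direction in this cohort can be derived from the documents.

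The point does not reach latest-line effects adjusted for progression at line start, time to first progression, or the powered within-PRRT change analyses. It is a worthwhile correction rather than a fault that invalidates the study.

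**What to change.** In 9.3, for sequence comparisons on overall survival and HRQoL (and creatinine clearance where applicable):

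- Define the strategies explicitly, for example A then B at progression versus A then C at progression, and only for the few common sequences with adequate numbers.
- Estimate them by inverse-probability weighting for adherence to the strategy, or by the parametric g-formula. Take the weights from line-specific treatment models, which 9.1.2 already plans in multinomial form, fitted among patients who reach that decision point. Include progression status and date, laboratory values, and survey scores where available.
- Do not condition on post-baseline progression in the outcome model. Truncate the weights and report balance and positivity.
- Keep the 9.3 time-dependent regression as a sensitivity analysis, limited to latest-line effects.

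**Cost.** Revised wording and moderate analyst time. Dated progressions are already needed for the PFS outcome in 7.2. Intervals will be wider, results will depend on the weight model, and rare sequences drop out. With about 180 PRRT patients expected to have complete HRQoL data (9.2.1), few sequences will support HRQoL weights. Symptom scores will often be missing at early line starts: surveys begin at enrolment, first enrolment was projected for April 2022 (Table 8, B12), and eligible diagnoses date from January 2019. Weighting does not remove confounding by prognosis that is not measured.
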